7.1 DEFINITIONS

Adverse Event (AE): any untoward medical occurrence in a patient or clinical study participant.

Serious Adverse Event (SAE): any untoward and unexpected medical occurrence or effect that:

- **Results in death**
- **Is life-threatening** – *refers to an event in which the participant was at risk of death at the time of the event; it does not refer to an event which hypothetically might have caused death if it were more severe*
- **Requires hospitalisation, or prolongation of existing inpatients' hospitalisation**
- **Results in persistent or significant disability or incapacity**
- **Is a congenital anomaly or birth defect**

Medical judgement should be exercised in deciding whether an AE is serious in other situations. Important AEs that are not immediately life-threatening or do not result in death or hospitalisation but may jeopardise the participant or may require intervention to prevent one of the other outcomes listed in the definition above, should also be considered serious.

7.2 REPORTING PROCEDURES

All adverse events should be reported. Depending on the nature of the event the reporting procedures below should be followed. Any questions concerning adverse event reporting should be directed to the Chief Investigator in the first instance.

7.2.1 Non serious AEs

All such events, whether expected or not, should be recorded.

7.2.2 Serious AEs

An SAE form should be completed and faxed to the Chief Investigator within 24 hours. However hospitalisations for elective treatment of a pre-existing condition do not need reporting as SAEs.

All SAEs should be reported to the Brent REC where in the opinion of the Chief Investigator, the event was:

- 'related', ie resulted from the administration of any of the research procedures; and
- 'unexpected', ie an event that is not listed in the protocol as an expected occurrence

Reports of related and unexpected SAEs should be submitted within 15 days of the Chief Investigator becoming aware of the event, using the NRES SAE form for non-IMP studies. The Chief Investigator must also notify the Sponsor of all SAEs.

Local investigators should report any SAEs as required by their Local Research Ethics Committee, Sponsor and/or Research & Development Office.

Contact details for reporting SAEs

[contact]

CI email (and contact details below)

Please send SAE forms to: [contact] [contact] (Mon to Fri
09.00 – 17.00)

8. ASSESSMENT AND FOLLOW-UP

Participants will be followed-up for the 24 weeks of the study.

8.1 LOSS TO FOLLOW-UP

Participants lost to follow-up will be flagged by the research team and removed from the study.

8.2 TRIAL CLOSURE

This study will be closed after the last patient completes their week 24 visit and data entry is completed.

8. STATISTICS AND DATA ANALYSIS

A study master list with patient identifiable information will be stored on a password-protected NHS computer in a locked research office at Queen Charlotte's and Chelsea Hospital, accessible only to the research team. This will match patient identifiable information with their study identification number. This study identification number will be used for the study database, which will be a cloud-based Excel database, which will be password protected and accessible only by the research team.

If any health conditions are discovered incidentally during the study they would be discussed with the participant immediately and their consent sought to share the information with their GP for the arrangement of their ongoing healthcare.

The study sample is 50 participants, 25 in each arm. The sample size has been based on guidance from the NIHR on pilot/feasibility studies (12) and the literature that it references that concludes that pilot studies should look for a sample size of at least 50 (13).

Data will be analysed after all participants have completed the 24 study weeks and all data is collected. Patient demographics will be presented as median/range or as categorical data where appropriate. We will evaluate primary and secondary outcomes using descriptive statistics. Between group comparison will be made using logistic regression.

Data and all appropriate documentation will be stored for 10 years after the completion of the study in accordance with ICHT guidance.

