8.2 TRIAL CLOSURE

9. STATISTICS AND DATA ANALYSIS

10. MONITORING

GLOSSARY OF ABBREVIATIONS

RCT	Randomised Controlled Trial
GDM	Gestational Diabetes Mellitus

POST-GDM-DNA; Post-delivery intervention for weight loss, glycaemia and cardiovascular health

IRAS ID 292085

Protocol v12.1 8/3/22

CI	Chief investigator
TMG	Trial Management Group
GCP	Good clinical practice
HbA1c	Glycated haemoglobin - monitors average blood glucose
HDL	High-density lipoprotein cholesterol
LDL	Low-density lipoprotein cholesterol
BP	Blood pressure

KEYWORDS

Weight, blood pressure, glycaemia, HbA1c, physical activity, wearable, postnatal, post-delivery, DNA, personalised

STUDY SUMMARY

TITLE Post-delivery intervention in women with previous gestational diabetes mellitus for weight loss, glycaemia and cardiovascular health

DESIGN Feasibility study

Allocation: RCT

AIMS To determine the feasibility of a post-delivery intervention to improve glycemia and cardiovascular function and promote weight loss in women who have had gestational diabetes.

OUTCOME MEASURES Primary outcome; Effect of intervention on HbA1c: difference in HbA1c between intervention arm and control arm measured at 12 weeks.

Secondary Outcomes;

- Adherence to intervention;
- Willingness to be randomised to post-delivery intervention;
- Process measures to evaluate patient experience of study and intervention;
- Participants' preferred time to commence the study, within the start date allowance of 6 weeks – 6 month post-delivery.
- Between-arm differences and within-arm differences to evaluate:
 - Effect of intervention on HbA1c at 12 and 24 weeks
 - Effect of intervention on weight and BMI at 12 and 24 weeks
 - Effect of intervention on systolic and diastolic blood pressure at 12 and 24 weeks
 - Effect of intervention on lipid profile (total cholesterol, HDL, LDL) at 12 and 24 weeks
 - Effect of intervention on physical activity at 12 and 24 weeks

POPULATION We will recruit 50 women aged 18-45 with previous gestational diabetes and randomise them to 1 of 2 arms to commence study at 6 weeks – 6 months post-delivery. Women starting the study at 13 weeks post-delivery will have their routine post-delivery HbA1c act as baseline HBA1c.

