3. STUDY DESIGN

We will conduct a feasibility study for an open-label, randomised, controlled trial of a personalised post-delivery intervention (*DNA Nudge*) to improve weight, glycaemia and cardiovascular function in women with previous GDM.

The study is designed to be remote, to enable the study to begin and continue in the pandemic and minimise barriers to recruitment. Study participants will be provided with equipment and instructions to collect samples and measurements at home. Contact with the research team will be over telephone or Microsoft Teams video call.

We will advertise in diabetes antenatal clinics using word-of-mouth, posters, social media and on departmental emails at Imperial College Healthcare NHS Trust or Imperial College POST-GDM-DNA; Post-delivery intervention for weight loss, glycaemia and cardiovascular health IRAS ID 292085

for women with current/previous GDM aged 18-45. We will recruit via Twitter, email and in-person encounters.

We will randomise women to 1 of 2 arms:

Arm 1: Standard dietary and physical activity advice as per NICE guidelines at week 1 (active control arm; n = 25)

Arm 2: DNA-based personalised dietary and physical advice delivered by DNA Nudge dietician at week 1 and by DNA Nudge wearable and app for weeks 1-24 (intervention arm; n = 25)

Women not randomised to DNA Nudge will be provided with an activity app/wearable device (Fitbit) to monitor daily step count. All women will be provided with a home BP monitor and weighing scales.

Week 1

Eligibility assessment, consent, randomisation, IPAQ questionnaire, baseline BP and weight, blood sample collected for baseline lipid profile.

Some women will begin the study at 13 weeks post-delivery and coincide with the routine postnatal HbA1c for women with GDM. The routine post-delivery HbA1c will be baseline HbA1c for this study. For women who commence the study outside the 13 weeks post-delivery window, a finger prick blood sample will be used for a baseline HbA1c test.

Women in the control arm will be given standard dietary and physical activity advice by the research team, in line with NICE guidelines.

Women in the DNA Nudge arm will provide a cheek swab for DNA analysis, carried out by DNA Nudge. They will be given personalised dietary advice by a DNA Nudge dietician, and be provided with DNA Nudge wearable, app and instructions.

Week 6:

Telephone/video-call follow-up to check ongoing willingness to participate and assess adherence.

Week 12:

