Collect weight and BP data from weeks 1-12, collect blood sample for HbA1c and lipid profile. Check ongoing willingness to participate and assess adherence.

Week 18:

Telephone/video-call follow-up to check ongoing willingness to participate and assess adherence.

Week 24:

Collect weight and BP data from weeks 12-24, follow-up IPAQ questionnaire, collect blood sample for HbA1c and lipid profile, return devices and collect usage data from DNA Nudge. Qualitative questionnaire to explore intervention experience.

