4. PARTICIPANT ENTRY

4.1 PRE-RANDOMISATION EVALUATIONS Women replying to our adverts will be assessed for eligibility by questionnaire.

4.2 INCLUSION CRITERIA Pregnant women with gestational diabetes (women will be given the option to start the study between 6 weeks and 6 months post-delivery) or women who have given birth in the last 12 months and had gestational diabetes during that pregnancy, aged 18-45, access to a smartphone with an operating system of iOS 9.0 or above, or Android 5.0 or above [CB: operating systems correct as of 23/03/21]

4.3 EXCLUSION CRITERIA Diabetes outside of pregnancy (diagnosis of type 1 or 2 diabetes; or HbA1c 48 mmol/mol or above). Health contra-indications to moderate-vigorous exercise. Planning pregnancy during the study period or become pregnant during the study period. Cancer, kidney disease, liver disease, or pancreatitis. Have had gastric bypass surgery or similar weight loss surgery.

4.4 WITHDRAWAL CRITERIA If women withdraw consent or become pregnant during the study period, the data collected to that point will be retained, they will be withdrawn from the study and we will request permission to collect safety outcomes from them.

If they agree to participate, consent will be gained and stored in the site file.

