5. RANDOMISATION AND ENROLMENT PROCEDURE

This will be an open-label trial. Randomisation will be in a 1:1 ratio by serially numbered, sealed, opaque envelopes, which will be prepared by a member of staff outside the research team.

Randomisation will be stratified by breastfeeding status (yes/no) at the time of recruitment.

5.1 RANDOMISATION OR REGISTRATION PRACTICALITIES Sealed envelopes will kept in a locked filing cabinet in a research office at Queen Charlotte's and Chelsea Hospital. Randomisation will occur in person at the QCCH site.

5.2 UNBLINDING This will be an open-label study. Data analysis will be study-arm blinded, unblinding will occur after completion.

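### Logistic regression is the only between-arm model named, but the primary outcome is a difference in HbA1c, so nothing in the plan estimates that difference with an interval

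*Combined protocol and SAP*

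**What the plan says.** The outcome list in the Study Summary gives the primary outcome as "Effect of intervention on HbA1c: difference in HbA1c between intervention arm and control arm measured at 12 weeks". The secondary list asks for between-arm and within-arm differences in HbA1c, weight and BMI, systolic and diastolic blood pressure, total, HDL and LDL cholesterol, and physical activity, each at 12 and 24 weeks. Section 2 repeats these as objectives, without BMI.

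The Statistics and Data Analysis section (numbered 8 in the text, 9 in the contents list) covers the analysis of outcomes in two sentences: "We will evaluate primary and secondary outcomes using descriptive statistics", followed by "Between group comparison will be made using logistic regression". It gives no response variable, covariates, effect measure, confidence interval or significance level.

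The only HbA1c threshold is the exclusion in section 4.3, "or HbA1c 48 mmol/mol or above", which is an entry rule and not an outcome. Section 3 provides for a baseline HbA1c, either the routine postnatal test or, outside that window, "a finger prick blood sample will be used for a baseline HbA1c test". Section 5 states: "Randomisation will be stratified by breastfeeding status (yes/no) at the time of recruitment". The analysis text uses neither the baseline value nor the stratum.

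**The concern.** Logistic regression needs a binary response, and the primary outcome is a difference on a continuous scale. An analyst who obeys the sentence has to invent something the plan does not contain: a cut-point for HbA1c, or a reversed model with arm as the response. Neither returns the quantity that the Study Summary defines.

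In a feasibility study of 50 women, the useful results for planning a later trial are the size of the HbA1c difference and its precision. The named model supplies neither. The choice between dichotomising (and where) and reversing the regression would be made with the outcome data in hand.

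**Working it through.** **Sample size.** The plan offers one figure to reproduce, 25 + 25 = 50, and it agrees. N rests on general guidance for pilot studies. The documents give no SD, effect size, power, alpha or baseline correlation, so the figures below use assumed values and show the effect of following the sentence, not forecasts.

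**Step 1. Outcome against model**

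| Outcome | Scale | Binary form defined? | Between-arm model named |
|---|---|---|---|
| HbA1c, 12 weeks (primary) and 24 weeks | continuous | no | logistic |
| Weight, BMI | continuous | no | logistic |
| Systolic and diastolic BP | continuous | no | logistic |
| Total cholesterol, HDL, LDL | continuous | no | logistic |

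**Step 2. Reading 1: dichotomise.** The cuts are ours. For normal data split so that a proportion p has the event, efficiency relative to comparing means is φ(z_p)² / [p(1−p)].

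- p = 0.5: 0.637; 0.637 × 50 = 31.8 women
- p = 0.2: 0.490; 0.490 × 50 = 24.5 women
- p = 0.1: 0.342; 0.342 × 50 = 17.1 women

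With no effect and p = 0.1, the chance that at least one arm has no events is 1 − (1 − 0.9^25)² = 0.138. An ordinary logistic odds ratio is then not finite.

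With a split midway between the arm means, 25 per arm and a two-sided 5% test, power falls from 81% to 60% at a 0.8 SD difference and from 42% to 28% at 0.5 SD. At unequal cuts the loss depends on direction. For an assumed 0.81 SD difference (about 80% power by t-test):

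| Control proportion | Event becomes rarer | Event becomes more common |
|---|---|---|
| 20% | to 4.9%; power 42% | to 48.7%; power 60% |
| 10% | to 1.8%; power 31%; an arm without events in 66% of trials | to 31.9%; power 51%; an arm without events in 7% of trials |

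**Step 3. Reading 2: regress arm on HbA1c.** In simulation (4,000 trials per setting, 25 per arm, 0.81 SD) power is about 82%, against 80% for the t-test, so there is no loss. The difficulty is the effect measure. With normal data and equal variance, the odds ratio per mmol/mol is exp(δ/SD²). For δ = 2 mmol/mol:

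- SD 3: exp(2/9) = 1.249
- SD 4: exp(2/16) = 1.133
- SD 5: exp(2/25) = 1.083

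One HbA1c difference thus gives three different odds ratios.

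**Step 4. A linear model instead.** With 25 per arm, the unadjusted 95% CI half-width is t(0.975, 48) × √(2/25) = 0.569 SD. For an assumed SD of 3 to 5 mmol/mol that is 1.7 to 2.8 mmol/mol. Adjusted for baseline and stratum, it is t(0.975, 46) × √(2/25) × √(1 − ρ²):

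| Assumed baseline to week-12 correlation ρ | 0.3 | 0.5 | 0.7 | 0.8 |
|---|---|---|---|---|
| Half-width (SD) | 0.543 | 0.493 | 0.407 | 0.342 |

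With losses, the unadjusted half-width is 0.61 SD at 22 per arm and 0.64 SD at 20.

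**The case against.** The best defence is that this is a feasibility study with no power target, and that the outcomes are assigned to descriptive statistics. Arm means, SDs and a raw HbA1c difference fall under that heading and come close to the primary outcome as worded. The logistic sentence names no outcome and may have been meant for adherence or willingness to be randomised. Nobody proposes dichotomising. The reversed regression costs no power, and its odds ratio can be turned roughly back into a difference if the SD is reported. Section 5.2 keeps the analysis blind to arm, which limits scope for favouring one. An unadjusted linear model with an interval would cure the mismatch, and covariate adjustment is a separate preference.

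Much of this is fair. The raw difference is probably not lost, blinding to arm tempers the worry about choices made on the data, and the dichotomisation losses apply only if someone dichotomises. The precision figures for 25 per arm are also best case, because sections 4.4 and 8.1 withdraw or remove participants.

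The mismatch remains. The descriptive sentence commits to no mean difference and no interval, and the next sentence gives between-group comparison to logistic regression without limit. If that sentence was meant only for adherence or willingness, neither is defined as binary and the continuous outcomes then have no comparison model at all. Blinding to arm does not supply a missing cut-point or model.

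**Conclusion.** The concern holds and should be corrected before the arms are unblinded. The only comparison model named cannot estimate the primary outcome as the Study Summary defines it, and the same applies to the weight, BMI, blood pressure and lipid secondaries. This conclusion rests on the text alone.

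The size of the harm depends on how the sentence is followed. Dichotomising normal data would keep 64%, 49% or 34% of the information at 50%, 20% or 10% cuts. Reversing the regression would keep the power but report an odds ratio that changes with the SD. Cuts, SDs, differences and correlations are all assumed, since the documents state none.

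**What to change.** Replace the logistic regression sentence with wording such as:

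> The between-arm difference in week-12 HbA1c will be estimated by linear regression (ANCOVA) of week-12 HbA1c on arm, baseline HbA1c and breastfeeding stratum, and reported as an adjusted mean difference with 95% CI, beside the raw mean and SD in each arm. HbA1c at 24 weeks, and weight, BMI, systolic and diastolic BP, total cholesterol, HDL and LDL at 12 and 24 weeks, will be analysed in the same way, each with its own baseline, as will any continuous physical activity score that has a week-1 value. Logistic regression is kept for outcomes defined in advance as binary.

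The essential change is a linear model with an interval. Adjusting for baseline and stratum is recommended because it narrows the interval and reflects the randomisation.

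Four details should be settled in the same paragraph:

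- The stratum should be the one used at randomisation, since women may be recruited while pregnant, when breastfeeding status is not defined.
- The source of baseline HbA1c (routine test or finger prick) should be recorded.
- BMI needs height, which the Week 1 list in section 3 does not mention, although BMI is already a listed outcome.
- Section 3 schedules the IPAQ at week 1 and a "follow-up IPAQ questionnaire" at week 24, so a week-12 activity analysis needs another named measure.

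The cost is one paragraph of wording. No extra participants are needed, and the data are either already collected or required by outcomes that the plan already lists.

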10. MONITORING

10.1 RISK ASSESSMENT

This study uses a commercially available DNA analysis product used in-keeping with the manufacturer's guidelines. This study recommends exercise in accordance with the UK Chief Medical Officer's recommendations. This study supplies commercially available products for home blood pressure, weight and activity monitoring. As such it is considered low risk.

11. REGULATORY ISSUES

11.1 ETHICS APPROVAL

The Study Coordination Centre has obtained approval from the Brent Research Ethics Committee (REC) and Health Regulator Authority (HRA). The study must also receive confirmation of capacity and capability from each participating NHS Trust before accepting participants into the study or any research activity is carried out. The study will be conducted in accordance with the recommendations

POST-GDM-DNA; Post-delivery intervention for weight loss, glycaemia and cardiovascular health
IRAS ID 292085

Protocol v12.1 8/3/22

for physicians involved in research on human subjects adopted by the 18th World Medical Assembly, Helsinki 1964 and later revisions.

11.2 CONSENT

Consent to enter the study must be sought from each participant only after a full explanation has been given, an information leaflet offered and time allowed for consideration. Signed participant consent should be obtained. The right of the participant to refuse to participate without giving reasons must be respected. After the participant has entered the study the clinician remains free to give alternative treatment to that specified in the protocol at any stage if he/she feels it is in the participant's best interest, but the reasons for doing so should be recorded. In these cases the participants remain within the study for the purposes of follow-up and data analysis. All participants are free to withdraw at any time from the protocol treatment without giving reasons and without prejudicing further treatment.

As this study follows a remote design, the informed consent process will be either face to face or using an online eConsent platform provided by REDCap.

11.3 CONFIDENTIALITY

Participants' identification data will be required for the registration process. The Study Coordination Centre will preserve the confidentiality of participants taking part in the study and is registered under the Data Protection Act.

Blood and saliva samples will be anonymised. All samples will be destroyed during sample analysis. Research data and consent forms will be kept for 10 years after study completion.]

It will be necessary for DnaNudge Ltd to be transferred the following anonymised data:

- Genetic results
- Participant ID
- Year of Birth
- Sex

This is necessary in order for the algorithms of DnaNudge Ltd to compute the DNA-based dietary guidelines, the app and the wearable device that will be provided to participants in the intervention arm. Of note, DnaNudge Ltd will not receive the names of participants, the only data that will be transferred will be anonymised.

Buccal mucosal cells samples from the inner side of the cheek and the oral cavity of the participant will be processed in a small genetic testing device (NudgeBox). The end-to-end processing of the sample includes inserting the swab sample into the disposable cartridge, placing the cartridge in the NudgeBox and extracting DNA from the swab sample (a process that can be controlled by the participant's mobile device), amplifying DNA, and analysing genetic results. The sample-containing cartridge is single use only and is disposed upon completion of the test. The genetic analysis, carried out by the NudgeBox, will not examine the whole genetic sequence of the participant, but will be focuses on isolated partial genetic information (i.e. single-nucleotide polymorphism SNPs) that will give us an insight in how a participant is metabolises food, how different nutrients affect his/her body, and what impact different ingredients have on the participant in the long term. To the best of our knowledge, the genetic results provided by our test will not be informative enough to trace the personal details of an individual; furthermore, we will not perform any test to trace personal details. The genetic results, which are encrypted and protected by the password set by the participant, will be stored in the participant's mobile device App. The genetic results are also anonymised, encrypted, and backed-up in a password-protected and secure cloud service (i.e. AWS) maintained by DnaNudge when the mobile device is connected to the internet. The genetic results are separated from other data POST-GDM-DNA; Post-delivery intervention for weight loss, glycaemia and cardiovascular health

IRAS ID 292085

Protocol v12.1 8/3/22

in cloud storage and are secured by password-protected mechanism in which only the user can access his/her own results through the App using his/her log-in and participant ID.

If a participant would like to have all their data deleted, their account will be deleted in the cloud and they will not be able to access their App. All their data (such as genetic results and shopping records) and the back-up will be deleted in the cloud.

